An Interactive Response System (IRS) will provide study treatment group assignments (using a computer-generated randomization code provided by the IRS vendor) and dosing adjustments. An independent, unblinded Data Safety Monitoring Board (DSMB) will oversee the IRS and verify the appropriateness of all dosing adjustments, and monitor subject safety and the effectiveness of CTAP101 Capsules at regular intervals. Members of the DSMB will also conduct periodic reviews of study conduct to verify that all required data are captured to a sufficiently high degree (>95%) and within specified time frames (usually within 5 days), and to promptly recommend appropriate corrective actions to address any noted deficiencies, in an effort to minimize missing data. Specific responsibilities and activities of the DSMB will be defined in the charter ratified at the pre-study organizational meeting. These responsibilities will include the completion of an interim analysis of the data obtained in Cohort 1 to justify a starting dose for Cohort 2, and an interim analysis of the data obtained from Cohort 2 to justify a starting dose for a separate phase 2 study in subjects having ages of 1 month to <8 years.

Subjects receiving treatment prior to study enrollment with calcitriol or another 1 α -hydroxylated vitamin D analog, or calcimimetics prior to study enrollment will forgo further dosing with these agents for the duration of the study and complete an 8-week washout period prior to baseline assessments. Subjects receiving vitamin D supplementation at a rate above 1,700 IU/day or 50,000 IU (1,250 mcg) per month prior to study enrollment must reduce the dose to ≤1,700 IU/day for the duration of the study and undergo an 8-week washout period prior to baseline assessments if serum total 25-hydroxyvitamin D is ≥30 ng/mL. The washout period is unnecessary if serum total 25-hydroxyvitamin D is <30 ng/mL. Subjects will complete a 6-week follow-up (FU) period after completing the 26-week treatment period or after early termination (ET).

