Patient-Reported Palatability and Acceptability Assessments	
Patient-reported palatability and acceptability assessments will be performed at Visits 13 and 22 in accordance with the Schedule of Events (see APPENDIX 1). Age-appropriate assessments will be used based on already-established and standardized versions of the combined hedonic facial and 10 cm visual analog scale. Site staff will be trained to give standardized, age-appropriate, brief and clear instructions to the subjects or, where appropriate, to the parents/guardians.

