7.2 Treatment Period (Weeks 1-26)

7.2.1 Visits 4-10 (Days 8-71)

- May occur ± 3 days of scheduled day
- AE assessment
- Concomitant medications

- VS measurements
- Blood samples drawn for:
 - Chemistry (partial panel)
 - Plasma iPTH
 - Serum total 25-hydroxyvitamin D

7.2.2 *Visits 11-12 (Days 83-84)*

- Must occur on the scheduled days
- AE Assessment
- Concomitant medications
- VS measurements
- Blood samples drawn for all subjects at 0 (pre-dose), 6 and 12 hours and additionally, only for subjects assigned to intensive PK evaluation, at -2, 2, 4 and 8 hours after dosing on Day 83 for:
 - Chemistry (partial panel)
 - Serum 25-hydroxyvitamin D₃, [REDACTED]
- Blood samples drawn at 24 hours ±4 hours before dosing on Day 84 for:
 - Chemistry (partial panel)
 - Serum 25-hydroxyvitamin D₃, [REDACTED]

7.2.3 *Visit 13 (Day 85):*

- Must occur on the scheduled day
- Urine pregnancy (for females of childbearing potential)
- AE assessment
- Concomitant medications
- Urine pregnancy (only for females of childbearing potential)
- VS measurement
- Urine chemistry and urinalysis
- Blood samples drawn at 48 hours ±4 hours before dosing for:
 - Chemistry (full panel) and hematology
 - Plasma iPTH
 - Serum total 25-hydroxyvitamin D
 - Serum 25-hydroxyvitamin D₃, [REDACTED]
 - [REDACTED]
- Drug accountability
- Patient reported palatability and acceptability

- Dispense assigned bottles of study drug

7.2.4 *Visits 14-21 (Days 92-169)*

- May occur ± 3 days of scheduled day
- Visits 14 and 16 are required only for subjects who underwent upward dose titration at visit 13
- AE assessment
- Concomitant medications
- VS measurements
- Blood samples drawn for:
 - Chemistry (partial panel)
 - Plasma iPTH
 - Serum total 25-hydroxyvitamin D

7.2.5 *Visit 22 (Day 183):*

- Must occur on the scheduled day
- Urine pregnancy (only for females of childbearing potential)
- AE assessment
- Concomitant medications
- VS measurements
- Urine chemistry and urinalysis
- Blood samples drawn for:
 - Chemistry (full panel) and hematology
 - Plasma iPTH
 - Serum total 25-hydroxyvitamin D
 - Serum 25-hydroxyvitamin D₃, [REDACTED]
 - [REDACTED]
- Patient reported palatability and acceptability
- Drug accountability

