7.3 Follow-up Period or Second PK Assessment

7.3.1 *Visit 23 (Day 190)*

- Must occur on the scheduled day
- Required only for subjects participating in the second PK assessment
- AE Assessment

- Concomitant medications
- VS measurements
- Blood samples drawn for:
 - Chemistry (partial panel)
 - Serum 25-hydroxyvitamin D₃, [REDACTED]

7.3.2 *Visit 24 (Day 197)*

- May occur ± 3 day of scheduled day
- Required only for subjects participating in the second PK assessment
- Concomitant medications
- AE assessment
- VS measurements
- Blood samples drawn for:
 - Chemistry (full panel) and hematology
 - Plasma iPTH
 - Serum total 25-hydroxyvitamin D
 - Serum 25-hydroxyvitamin D₃, [REDACTED]

7.3.3 *Visits 25-27 (Days 204-218)*

- Must occur on the scheduled days
- Required only for subjects participating in the second PK assessment
- AE Assessment
- Concomitant medications
- VS measurements
- Blood samples drawn for:
 - Chemistry (partial panel)
 - Serum 25-hydroxyvitamin D₃, [REDACTED]

7.3.4 *Visit 28/ET (Day 225)*

- May occur ± 3 day of scheduled day
- Concomitant medications
- AE assessment
- PE (including weight, height and BMI)
- VS measurements
- 12-lead ECG

- Urine chemistry and urinalysis
- Urine pregnancy (only for females of childbearing potential)
- Blood samples drawn for:
 - Chemistry (full panel) and hematology
 - Plasma iPTH
 - Serum total 25-hydroxyvitamin D
 - Serum 25-hydroxyvitamin D₃, [REDACTED]
 - [REDACTED]

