9.2 Determination of Sample Size

Sample size has been calculated (using Fisher's exact test statistics) to provide power of 80% for a two-sided, alpha 0.05 level test of equal proportions comparing the percentages of subjects attaining a mean decrease of at least 30% in plasma iPTH (averaged over the last 6 weeks of treatment) compared to baseline on daily dosages of CTAP101 Capsules (active) versus placebo. Assuming response rates of at least 0.4 (CTAP101 Capsules) versus 0.1 (placebo), and using a 2:1 ratio of CTAP101 Capsules:placebo subjects with an estimated 20% dropout rate over the course of the study, a sample size of approximately 108 subjects is required in the study with two-thirds apportioned to the 12 to <18 year age group (Cohort 1) and one-third apportioned to the 8 to <12 year age group (Cohort 2), allocated as 72 subjects to CTAP101 Capsules and 36 subjects to placebo.

No subject replacement is planned.

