9.12 Other Analysis

Descriptive statistics will be applied to evaluate patient reported palatability and acceptability. In addition, the proportion of subjects attaining the mean decrease from baseline in plasma iPTH of $\geq 30\%$ in the subgroup of subjects with and without nutritional intake within 60 minutes of medication administration will be evaluated using the analysis methods described above.

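### Palatability and acceptability are scored only at Visits 13 and 22 and not at early termination, so a child who stops study drug before Day 85 is never scored

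*Combined protocol and SAP*

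**What the plan says.** Section 6.3, Table 1, fixes the timing: "Patient-reported palatability and acceptability assessments will be performed at Visits 13 and 22 in accordance with the Schedule of Events". The visit lists agree. Sections 7.2.3 (Visit 13, Day 85) and 7.2.5 (Visit 22, Day 183) each carry the item "Patient reported palatability and acceptability", and Appendix 1 marks it at those two visits and nowhere else.

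It is absent from Visits 4–12, Visits 14–21 and all follow-up visits. Visits 23–27 are in any case restricted: "Required only for subjects participating in the second PK assessment". Visit 28/ET (Section 7.3.4) collects physical examination, weight, height, BMI, ECG, urine tests and blood samples, but not this scale.

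Under Section 3.1, a subject who terminates early goes into the six-week follow-up. No text brings such a subject back for Visit 13 or Visit 22.

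The analysis is one sentence in Section 9.12: "Descriptive statistics will be applied to evaluate patient reported palatability and acceptability". It has no rule for subjects without a score. The sensitivity and tipping-point analyses in Section 9.6 are directed at the primary efficacy and safety endpoints and at the effect of discontinuations on the study's conclusions. They do not mention this assessment.

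**The concern.** For most descriptive measures, a missing end-of-study value is a nuisance. Here the reason for the missing value may be the value itself: a child who finds the capsules hard to swallow or unpleasant has a direct motive to stop, and stopping before Day 85 removes that child from the table. If some early stops are of this kind, the reported distribution is shifted toward good acceptability, and nothing in the planned output would show it.

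The protocol says in Section 1.13 that the product has not previously been studied in pediatric patients, so this summary will be early evidence on whether children accept it. The other recorded information is a weak substitute. Capsule counts are also taken only at Visits 13 and 22 (Section 6.5), and the termination reasons in Section 9.6 include no category for taste, swallowing or refusal.

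**Working it through.** The plan gives no figure for unscored subjects, so there is none to reproduce. The calculation below gives the scale only.

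**Inputs**
- Randomized: 108 subjects, 72 active and 36 placebo (Section 9.2).
- Dropout: "with an estimated 20% dropout rate over the course of the study" (Section 9.2). Its timing is not given.
- Days elapsed since Day 1: 84 at Visit 13 (Day 85), 182 at Visit 22 (Day 183) and 224 at Visit 28 (Day 225).
- Assumption: dropout stands in for stopping study drug, and a subject who drops out attends no later assessment visit.

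**Never scored (stopped before Visit 13)**

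| Timing of the 20% | Formula | Share | Of 108 |
|---|---|---|---|
| All after Visit 13 | 0 | 0% | 0 |
| Even over 32 weeks, including follow-up | 0.20 × 84/224 | 7.5% | 8.1 |
| Even over the 26 treatment weeks | 0.20 × 84/182 | 9.2% | 10.0 |
| Constant hazard over 26 weeks | 1 − 0.80^(84/182) | 9.8% | 10.6 |
| All before Visit 13 | 0.20 | 20% | 21.6 |

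In the 26-week even case, the split at equal dropout rates is 72 × 0.0923 = 6.6 active and 36 × 0.0923 = 3.3 placebo.

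**No Visit 22 score**
- Even over 32 weeks: 0.20 × 182/224 = 16.3%, and 108 × 0.1625 = 17.6, about 18 subjects.
- All dropout within the 26 treatment weeks: 0.20 × 108 = 21.6, about 22 subjects.

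**Largest possible effect on the summary.** If a share f is unscored, the all-subject acceptable rate is (1 − f) × (rate in scored) + f × (rate in unscored). The documents give neither rate. Assume, for illustration only, that 90% of scored children find the capsules acceptable and none of the unscored would:
- f = 7.5%: 0.925 × 90% = 83.3%.
- f = 9.2%: 0.908 × 90% = 81.7%.
- f = 20%: 0.80 × 90% = 72%.

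If the unscored children resemble the scored ones, the figure stays at 90%. The real answer lies between these extremes, and the planned data cannot locate it.

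**The case against.** The strongest reply is about weight. Palatability is neither a study objective (Section 2.1) nor a primary or secondary endpoint (Sections 9.8.1–9.8.4). It is an additional assessment (Section 9.9), reported descriptively. Visits 13 and 22 are also the drug-accountability visits, so the timing is coherent. All of this stands, and it keeps the point minor.

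A second reply is that refusal is not invisible. Section 9.6 tabulates reasons for termination, including non-compliance, withdrawal of consent and a free-text Other. This stands in part: a reason for stopping is recorded, but it is not a rating, and a palatability reason could be spread over several categories.

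A third reply limits the remedy. The protocol describes no separate visit on stopping drug. If the ET visit closes the six-week follow-up, the child would be rating from memory. Subjects lost to follow-up, or who withdraw consent, may never be reached. This also stands and shapes the fix.

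A reader might infer three stronger things that the documents do not support:
- **That the result covers only children who tolerated the product.** The scored group is everyone still attending. It can include children who dislike the capsules but continue, and poor compliers, since compliance below 80% is reported as a deviation (Section 5.10) and does not in itself remove the subject. Their poor scores would be captured.
- **That the summary is biased, and more so in Cohort 2.** Many of the listed reasons for stopping, such as dialysis, disease progression, pregnancy or a fifth dose reduction, have no evident link to palatability. No figure in the plan shows the direction or size of a bias, or a difference between cohorts.
- **That about 22 subjects will be missing.** The 20% applies to the whole study, including follow-up, so 22 is an upper bound.

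**Conclusion.** The gap is real. It is consistent across Table 1, the visit lists and Appendix 1, so it is a feature of the design and not a slip in one place. Whether it biases the summary depends on why children stop. The plan neither collects a score at stopping nor commits to reporting the number unscored, so a reader of the results could not judge this.

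On even dropout, the loss is just under one in ten subjects at Visit 13 and about one in six to one in five at Visit 22. Both figures rest on the planned 20% being realized, on the assumed timing, and on dropout standing for stopping study drug. This is a low-cost improvement of low weight.

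**What to change.** **Collection.** In Table 1, Section 7.3.4 and Appendix 1, add the same scale for any child who stops study drug before Visit 22. Take it at the first contact after stopping, or at the ET visit if there is no earlier contact, and record the days since the last dose. Add a palatability, swallowing or refusal category to the termination reasons in Section 9.6, or code it from the free text, so that such stops can be counted.

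**Analysis.** In Section 9.12:
- keep the Visit 13 and Visit 22 tables;
- add a summary of the last available score, with early-stopping scores shown separately from on-treatment scores so that recall off drug is not pooled with current experience;
- report by arm the number unscored and the number who stopped because of palatability, swallowing or refusal.

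**Cost.** The change takes a few minutes per early stopper, for at most about 22 subjects at the planned dropout, plus one form entry and one table. Table 1 already provides for age-appropriate versions of the scale and for staff training. Ratings given off drug will carry some recall error, and subjects lost to follow-up will not be recovered, which is why the unscored count should be reported in any case.

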6.4 Clinical Laboratory Tests

6.4.1 *Laboratory Parameters*

Blood will be drawn and analyzed as specified in [Table 2](#) List of Laboratory Tests. [REDACTED]

[REDACTED]. All serum calcium values will be adjusted based on serum albumin level of <4.0 g/dL. Urine samples will be collected and analyzed as specified in Table 2 List of Laboratory Tests.

Please refer to [Appendix 1](#) Schedule of Events for specific visits when each laboratory parameter will be determined.

All clinically significant laboratory values will be recorded as AEs and the investigator will FU according to [Section 6.6.7](#) Clinical Significance.

Subjects will be in a seated position during blood collection.

Table 2. List of Laboratory Tests

Hematology:	Serum Full Chemistry:
Hematocrit	Albumin
Hemoglobin	Alkaline phosphatase
Mean corpuscular hemoglobin	Alanine aminotransferase (ALT) / Serum glutamic-pyruvic transaminase (SGPT)
Mean corpuscular hemoglobin concentration	Aspartate aminotransferase (AST) / Serum glutamic-oxaloacetic transaminase (SGOT)
Mean corpuscular volume	Blood urea nitrogen
Platelet count	Calcium (corrected for serum albumin)
Red blood cell count	Carbon dioxide
White blood cell count	Chloride
Urine Chemistry and Urinalysis:	Creatinine*
Albumin	Gamma-glutamyl transferase
Albumin/Creatinine ratio	Globulin
Appearance	Glucose
Bilirubin	Lactate dehydrogenase
Calcium	Phosphorus
Calcium/Creatinine ratio	Potassium
Color	Sodium
Creatinine	Total bilirubin
Glucose	Direct bilirubin
Ketones	Total cholesterol
Nitrite	Total protein
Occult blood	Triglycerides
pH	Uric acid
Phosphorus	
Protein	
Specific gravity	
Urobilinogen	
Urine pregnancy test (only for females of childbearing potential)	Serum Partial Chemistry:
	Calcium (corrected for serum albumin)
	Phosphorus
	Albumin
	Plasma iPTH (blinded)
	Serum total 25-hydroxyvitamin D (blinded)
	Serum 25-hydroxyvitamin D ₃ (blinded)

*Note: Visit 1 creatinine value to be used for eGFR calculation.

6.4.2 *Sample Collection, Storage, and Shipping*

Redraws for missing samples or samples resulting in values outside entrance criteria ranges should be performed during screening only. Any other missed samples at any other visits should not be redrawn and noted as not done in source documentation along with a reason. Laboratory samples not done should be noted as a protocol deviation.

A central laboratory experienced in clinical research studies will be utilized. Collection, processing, storage and shipping procedures will be performed in accordance with the instructions provided by the central laboratory. Detailed instructions will be provided separately from this protocol in the laboratory manual. Blood samples will be collected and analyzed for clinical laboratory [REDACTED] tests. Approximately 357 mL of blood will be collected over the entire duration of the study from each of the 15 subjects who provide intensive PK samples during the last three days of treatment week 12. Approximately 373 mL of blood will be collected over the entire duration of the study from each of the 20 subjects who provide PK samples during the post-treatment FU period. Approximately 323 mL of blood will be collected over the entire duration of the study from all other subjects.

Additional blood draws may be needed for unscheduled or repeat visits. Given the nature of this pediatric patient population, care should be taken with the amount of blood drawn at any one study visit or cumulative over a four week period.

[REDACTED]

[REDACTED]

[REDACTED]

Samples are to be shipped to the central laboratory for each subject as visits are completed. The investigator will provide a limited access, and a -20°C or lower freezer space for respective serum and plasma aliquots.

6.4.3 *Clinical Supplies*

The sponsor or assigned designee will supply vacutainers, blood collection tubes, labels, boxes with labels for storage of serum and plasma samples and all necessary shipping supplies/containers. The investigator will supply all phlebotomy and centrifugation equipment including biohazard and/or safety supplies. The investigator will ensure that all biohazard wastes are disposed of in accordance with investigator site standard operating procedures (SOPs) and local regulations.

6.5 Dispensing Study Drug

As described in [Section 5.6](#) Method of Assigning Subjects to Treatment Groups, the IRS will assign the study drug bottle(s) to the subject at the time of randomization (Visit 3) and at Visit 13. The study coordinator (or designated site personnel) will obtain the study drug assignment from the IRS for each subject and dispense the appropriate drug.

Subjects and their appointed guardians are to be instructed NOT to take study drug if it appears discolored or damaged. Subjects are to be advised that the study drug is to be stored at room temperature, 15-30°C (59-86°F). Protect from light and heat.

Subjects will receive a sufficient number of bottles of study drug at visits 3 and 13. Some bottles will contain CTAP101 Capsules and others may contain a matching placebo, dependent on

individual subject dose assignment. Throughout the treatment period the number of capsules remaining in the bottle will be counted by the investigator or designee and recorded on the drug accountability log at Visits 13 and 22. The bottles will then be returned to the subject. Prior to dispensing new bottle(s) of study drug, the coordinator will collect the previous bottle(s) of study drug. See [Section 5.3 Selection and Timing of Dose for Each Subject](#) for further details of drug dispensation.

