3.2 Rationale for Study Design and Control Group

EirGen is developing CTAP101 Capsules for the treatment of SHPT in pediatric patients with stages 3 or 4 CKD and VDI. The active ingredient in CTAP101 Capsules is calcifediol, which is formulated as ER capsules for oral administration.

The present study is designed to compare the efficacy of CTAP101 Capsules to matching placebo with regard to reducing mean plasma iPTH levels by at least 30% from pre-treatment baseline in pediatric patients with stage 3 or 4 CKD and VDI. The study will also examine the safety and tolerability of CTAP101 Capsules compared to placebo. This adequate and well-controlled, randomized and double-blind study provides the best means to evaluate efficacy, safety and tolerability of CTAP101 Capsules because no therapy has yet been approved by the FDA to treat elevated iPTH levels associated with low serum total 25-hydroxyvitamin D levels in pediatric CKD patients. In other studies conducted in adult subjects with stage 3 or 4 CKD and SHPT, administration of placebo therapy for 26-weeks has not been shown to result in untoward effects [Coyne 2006; Coburn 2004]. However, since iPTH values >900 pg/mL have been associated with increased risk of fracture in hemodialysis patients [Jadoul 2006], subjects will be terminated from this study for confirmed iPTH levels >900 pg/mL.

The starting dose of 30 mcg per day is based on the results from two phase 3 studies (CTAP101-CL-3001 and CTAP101-CL-3002) conducted in adults with SHPT, stage 3 or 4 CKD and VDI. Data from these studies demonstrated that steady-state serum 25-hydroxyvitamin D₃ levels were reached after 12 weeks of treatment at daily doses of 30 or 60 mcg of CTAP101 Capsules. Accordingly, upward dose titration is not allowed in the present study until after 12 weeks, when subjects receiving the initial dose of CTAP101 Capsules have attained steady-state blood levels of serum total 25-hydroxyvitamin D. A 26-week treatment period was selected for this study to ensure that steady-state will be attained in subjects who undergo upward dose titration at the beginning of treatment week 13.

Previous PK analyses in adult CKD patients have determined that the $t_{1/2}$ of serum 25-hydroxyvitamin D₃ is approximately 30 days (CTAP101-CL-2008). Consequently, the post-dosing FU period of 6-weeks should be sufficient for determining the $t_{1/2}$ in pediatric patients.

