5.3 Selection and Timing of Dose for Each Subject

Subjects in Cohort 1 will receive two capsules (CTAP101 Capsules and/or matching placebo capsules) every day at bedtime to achieve the targeted initial daily dose of 30 mcg of calcifediol (one CTAP101 Capsule plus one placebo capsule) or 0 mcg of calcifediol (two placebo capsules). Any food intake within 60 minutes of medication administration will also be recorded. At the end of 12 weeks of treatment, subjects assigned to active treatment will undergo upward dose titration to 60 mcg per day (two CTAP101 Capsules) provided that (a) plasma iPTH has not decreased by at least 30% from pretreatment baseline, (b) corrected serum calcium is <9.8 mg/dL, (c) serum phosphorus is \leq 5.5 mg/dL, and (d) serum total 25-hydroxyvitamin D is \leq 65 ng/mL. Subjects in Cohort 2 will receive a starting daily bedtime dose which will be determined on the basis of the interim analysis of data obtained in Cohort 1, and will undergo upward dose titration at the end of 12 weeks of treatment to a new daily dose that is two times higher than the starting dose, provided that (a) plasma iPTH has not decreased by at least 30% from pretreatment baseline, (b) corrected serum calcium is <9.8 mg/dL, (c) serum phosphorus is \leq 6.0 mg/dL and (d) serum total 25-hydroxyvitamin D is \leq 65 ng/mL.

In order to maintain blinding, subjects will receive periodic supplies of study drug in bottles of identical appearance, some labeled “Bottle 1” and some labeled “Bottle 2,” along with the same dosing instructions regardless of randomization group directing the subject to take one capsule from one bottle labeled “Bottle 1” and one bottle labeled “Bottle 2” every day at bedtime.

An unblinded medical monitor who will be part of the independent, unblinded DSMB will oversee study drug assignments and dose adjustments (see below) by IRS.

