5.12 Storage and Accountability

CTAP101 Capsules will be shipped to sites following standardized shipment and temperature monitoring procedures.

While at the study site, CTAP101 Capsules will be stored at room temperature, 15-30°C (59-86°F) in the supplied packaging, with access granted to authorized personnel only.

All sites must ensure that study drug has been kept under required conditions prior to dispensing. A temperature log recording the daily storage temperatures will be maintained at each site for study drug. Accountability for study drug, from receipt until final reconciliation and return of drug by the monitor or designee, will be the responsibility of the investigator or the assigned designee(s).

In the case of temperature excursions, products should not be dispensed and the investigator or the assigned designee(s) should contact the clinical monitor or the sponsor representative as soon as possible to receive further instructions.

The investigator or assigned designee(s), will maintain study drug accountability records for study drug throughout the course of the study. Specifically, the investigator or assigned designee will confirm that all study drug supplies are received intact and in the correct amounts per the shipping forms. This will be documented by signing and dating the shipping forms and providing a copy to the sponsor or designee. A study drug accountability and dispensing log will record the study drug disposition, including dates, quantity of drug received, to whom dispensed (participant-by-participant accounting), and accounts of any drug accidentally destroyed. The site's running inventory of study drug supplies will be verified routinely throughout the course of the study. All opened and unopened containers of CTAP101 Capsules bottles are to be retained at the site until the sponsor or designee has performed a complete verification of the dispensation, following which study drug will be returned to the sponsor or designee.

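### Section 6.5 hands counted bottles back to the subject at Visit 22 with no later collection step, against 5.12 and 5.13, and early termination has no drug accountability

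*Combined protocol and SAP*

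**What the plan says.** Section 6.5 (Dispensing Study Drug) sets the supply and count schedule. Supply is fixed by "Subjects will receive a sufficient number of bottles of study drug at visits 3 and 13". Counts are "recorded on the drug accountability log at Visits 13 and 22. The bottles will then be returned to the subject". The next sentence reads "Prior to dispensing new bottle(s) of study drug, the coordinator will collect the previous bottle(s) of study drug".

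Sections 7.2.3 and 7.2.5 and Appendix 1 agree with that schedule. Visit 13 (Day 85) has both accountability and dispensing. Visit 22 (Day 183) has accountability only. Visits 23 to 28/ET (7.3.1 to 7.3.4) list neither accountability nor any return of drug.

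Other sections assume that drug comes back. Section 5.12 states "All opened and unopened containers of CTAP101 Capsules bottles are to be retained at the site until the sponsor or designee has performed" its verification. Section 5.13 requires a final inventory and has the investigator send back all unused medication. Section 5.10 calculates compliance from the capsules returned and treats less than 80% as a protocol deviation.

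Section 5.3 gives every subject the same instruction throughout, "directing the subject to take one capsule from one bottle" of each label, Bottle 1 and Bottle 2. Section 3.2 relies on the period after Visit 22 to be free of study drug: "the post-dosing FU period of 6-weeks should be sufficient for determining the" half-life.

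**The concern.** A coordinator who follows 6.5 at Visit 22 counts the capsules and gives the bottles back, on the day the subject is meant to be finished with study drug. No later visit retrieves them. The household then holds surplus capsules, active if the child was on CTAP101, through six weeks that are supposed to be off drug. A coordinator who follows 5.12 keeps the bottles. Both would be following the protocol, so practice could differ between sites.

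Early stopping is a separate gap. Section 5.4 ends dosing for a subject who would need a fifth reduction and moves that subject into follow-up; others stop for the reasons in 6.8. None of them has a scheduled count or hand-in at that point, so compliance since the last count has no scheduled source.

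At Visit 13 the two sentences of 6.5 give opposite instructions. Old and new bottles carry the same labels. For a Cohort 1 subject titrated from 30 to 60 mcg/day, one label holds placebo in the first supply and both labels hold active drug in the second. If old bottles did stay at home, the dose taken could not be told from the label.

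**Working it through.** The plan states no figure for leftover drug. The main check is to set the text side by side; the counts after it are illustrative.

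**1. Is collection triggered at each visit?**

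| Visit | Count scheduled | New drug dispensed | 6.5 collection step applies | 6.5 hand-back applies |
|---|---|---|---|---|
| 13 (Day 85) | yes | yes | yes | yes (conflict) |
| 22 (Day 183) | yes | no | no | yes |
| 28/ET | no | no | no | no |

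At Visit 22 only the hand-back applies. Sections 5.12 and 5.13 point the other way but name no visit at which the subject gives up the last bottles. At ET there is no instruction at all.

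**2. How much drug could be left at Visit 22?**

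Inputs: 30 capsules per bottle (5.11); one capsule per label each night (5.3); Visits 13 and 22 must fall on their scheduled days (7.2.3, 7.2.5). Assumption: each supply is the smallest whole number of bottles that covers it, because 6.5 says only that the number is sufficient.

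Leftover per label = 30 × ceil(nights / 30) − adherence × nights.

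- First supply, Days 1 to 84: 84 nights, ceil(84/30) = 3 bottles, 90 capsules. Left: 90 − 84 = 6 at full adherence; 90 − 0.8 × 84 = 22.8 at 80%.
- Second supply, Days 85 to 182: 98 nights, ceil(98/30) = 4 bottles, 120 capsules. Left: 120 − 98 = 22 at full adherence; 120 − 0.8 × 98 = 41.6 at 80%.

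In Cohort 1 at full adherence, the active capsules held at Visit 22 are 22 for a subject on 30 mcg/day (one label active), 2 × 22 = 44 on 60 mcg/day, and none on placebo. A more generous supply, or days omitted under a dose reduction, would raise these numbers. The Cohort 2 starting dose is not yet set, so no active count is given for that cohort.

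**3. How long does the exposure window last?** Day 183 to Day 225: 225 − 183 = 42 days.

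**4. How many subjects could stop without a count?** 20% dropout (9.2) of 108 is 0.20 × 108 = 21.6, about 22. This is an upper bound: it places every dropout before Visit 22. Subjects who leave during follow-up have already been counted, and those who stop between Visits 13 and 22 have a Visit 13 count, though none at stopping.

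**5. Who matters for half-life?** Only the second PK subset, planned in 5.6 as 20 active-arm subjects per cohort.

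**The case against.** The best defence is that retrieval is plainly intended. Section 5.13 has all unused medication returned, 5.12 requires accounting participant by participant, and 5.10 speaks of returned capsules. On that view 6.5 contains a slip that sites would correct for themselves. This stands as to intent. It does not supply a visit for the last hand-in, and it leaves the sentence in 6.5 saying the opposite.

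Three stronger readings are tempting, and the documents do not support them.

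- *Children keep old capsules after the Visit 13 switch.* A reader might infer this from the hand-back sentence alone. The following sentence has "the coordinator will collect the previous bottle(s) of study drug" before new drug is given out, and Visit 13 is a dispensing visit. What remains there is a conflict between two sentences. Mixing of old and new bottles arises only if the collection sentence is not followed.
- *Compliance at Visit 22 is compromised.* The count is logged before the bottles are returned, so possession afterwards cannot change it.
- *The half-life estimate will be biased by a stated amount.* Any such figure needs subjects to keep dosing after treatment ends, which nothing tells them to do, and a particular curve fit, which the documents do not specify. Leftover drug makes an unrecorded dose possible in the second PK subset; its size cannot be derived from the plan.

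**Conclusion.** The point holds for Visit 22 and for early termination, and as an inconsistency at Visit 13. As written, 6.5 sends leftover study drug home for the 42-day follow-up, contrary to 5.12 and 5.13, and subjects who stop early (at most about 22 of 108) have no scheduled count or collection when they stop.

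The consequence is weaker drug accountability and avoidable possession of active capsules in homes with children, with a chance of unintended dosing. Planned dosing after Visit 22 is not implied. The efficacy assessment period ends at Visit 22, so the Visit 22 hand-back does not touch the primary efficacy endpoint. The PK relevance is confined to the second PK subset, and no bias figure is claimed.

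The reading of the text needs no assumption. The leftover counts rest on the smallest sufficient number of bottles and on the adherence shown. The point is worth correcting because the rule as stated gives a worse result than the one the other sections intend.

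**What to change.** - In 6.5, replace the hand-back sentence with a rule that all used and unused bottles are collected, counted and kept at the site at Visit 13 (before new bottles are dispensed), at Visit 22, and at the visit where dosing stops early.
- Add drug accountability to Visit 28/ET in 7.3.4 and in Appendix 1. State that for early stoppers the count is made at the visit where dosing ends, if that comes before the ET visit.
- Align 6.5 with 5.12 and 5.13 so that all three describe the same path from subject to site to sponsor.

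The cost is protocol wording, one more entry in the schedule, and a few minutes of site time when a subject stops early. No visit is added, and no dose or clinical rule changes.
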